13.2.1 Pulmonary Function Data Analyses

The Safety Analysis Set will be used for this analysis.

The absolute change from baseline in FVC and percent predicted FVC over time will be analyzed using the same MMRM as for FXIIa-mediated kallikrein activity, with treatment group, and visit as fixed effects, and baseline as a covariate. Interactions with visit will be included for treatment group and baseline. Mean difference in LSMeans between treatment groups and its 95% confidence interval will be provided at each time point, assuming that the data is normally distributed. If the data are not normally distributed by visual inspection of residual plots or statistical testing, an appropriate data transformation may be done. There is no imputation of missing FVC data planned.

For FVC and percent predicted FVC the observed values and absolute change from baseline will be summarized by nominal time point by descriptive statistics (n, mean, SD, minimum, Q1, median, Q3, maximum). The descriptive summary for both parameter will be provided for Safety Analysis Set and PD Analysis Set.

Mean (\pm SD) time profiles for observed values and absolute change from baseline for FVC and percent predicted FVC will be plotted by using nominal (planned) time points.

The number and proportion of subjects with $\geq 5\%$ or $\geq 10\%$ absolute (absolute change from baseline) or relative (percent change from baseline) decline in FVC percent predicted at Day 92 will be presented.

The absolute change from baseline in FVC at Day 92 versus the absolute change from baseline in FXIIa-mediated kallikrein activity at Day 92 will be graphically displayed by a scatter plot. The Pearson correlation coefficient and Spearman correlation coefficient by treatment group will displayed. Those scatter plots of absolute change in FVC at Day 92 versus the absolute change at Day 92 will be repeated for all PD parameter (FXII

concentration and aPTT) and biomarkers (CCL-18, PAI-1, SP-A, SP-D, YKL-40, PROC3, PROC6, C3M, C6M).

A second series of those scatter plots will be provided by using the percent change from baseline in FVC at Day 92 versus the percent change from baseline in PD parameter (FXIIa-mediated kallikrein activity, FXII concentration, aPTT) and biomarkers (CCL-18, PAI-1, SP-A, SP-D, YKL-40, PROC3, PROC6, C3M, C6M) at Day 92.

A third series of those scatter plots will be provided by using the absolute change in FVC percent predicted at Day 92 versus the absolute change from baseline in PD parameter (FXIIa-mediated kallikrein activity, FXII concentration, aPTT) and biomarkers (CCL-18, PAI-1, SP-A, SP-D, YKL-40, PROC3, PROC6, C3M, C6M) at Day 92.

A by-subject listing of FVC and percent predicted FVC including observed values, absolute and percent change from baseline will be provided.

14 References

(1) PK-GDL-01, Guideline on the Conduct of Noncompartmental Pharmacokinetic Analyses, CSL Behring.

15 Appendices

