The decline in FVC is an accepted measure of disease course and reliably predicts mortality in patients with IPF [[Paterniti et al, 2017](#); [Zappala et al, 2010](#); [Flaherty et al, 2003](#); [Collard et al, 2003](#); [Quinn et al, 2019](#)]. A decline in FVC of $\geq 10\%$ has been correlated with worse survival time in patients with IPF [[Paterniti et al, 2017](#); [Zappala et al, 2010](#); [Flaherty et al, 2003](#); [Collard et al, 2003](#)] and recent evidence-based guidelines state that an absolute decrease in FVC of $\geq 10\%$ over time is an acceptable method for assessing disease progression and estimate risk of future mortality in patients with IPF [[Raghu et al, 2011](#)]. Some studies suggest that an FVC decline $\geq 5\%$ may also be clinically significant [[Zappala et al, 2010](#); [du Bois et al, 2011](#)]. Using a relative (rather than an absolute) change in FVC has been shown to maximize the chance of identifying a $\geq 10\%$ decline without sacrificing prognostic accuracy [[Richeldi et al, 2012](#)]. The change in FVC has been used as the primary endpoint in several randomized controlled studies in subjects with IPF [[Raghu et al, 2008](#); [Raghu et al, 2012](#)] including those for the approved drugs nintedanib and pirfenidone [[Richeldi et al, 2014](#); [Noble et al, 2011](#)].

This study is a 14-week, placebo-controlled study. In both the INPULSIS studies and the INBUILD study with nintedanib in patients with IPF and progressive fibrosing interstitial lung diseases, respectively, a clear difference in the mean change in FVC from Baseline between the nintedanib groups and the placebo group is apparent at 12 weeks [Richeldi et al, 2014 (INPULSIS 1 and INPULSIS 2); Flaherty et al, 2019 (INBUILD)]. Similarly, a treatment effect is evident at Week 13 in the ASCEND study with pirfenidone in patients with IPF [King et al, 2014]. This study will determine if the FVC is altered by treatment with CSL312 over a 14-week period in patients with IPF.

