6.2 Safety Analysis Set

The Safety Analysis Set comprises all subjects who receive any portion of an IV infusion or SC injection of CSL312 or placebo, and analyses will be based on the actual treatment received.

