6.4 Pharmacodynamic Analysis Set

The PD Analysis Set is defined as subjects in the Safety Analysis Set for whom analysis results are obtained for ≥ 1 of the exploratory biomarkers of interest.

7 General Considerations

Datasets will be created according to clinical data interchange standards consortium (CDISC) standards. Study data will be provided in study data tabulation model (SDTM) format. Analysis data will be provided in analysis data model (ADaM) format.

SAS version 9.4 or higher will be used to perform all data analyses.

Summaries of continuous variables will be in terms of the number of observations, mean, SD, median, first quartile (Q1), third quartile (Q3), minimum and maximum. Other descriptive statistics (eg, standard error, CV) may be reported when appropriate. Categorical variables will be summarized using frequency counts and percentages. Analyses that use other descriptive statistics will have the specific descriptive statistics identified with the analysis in the applicable SAP section.

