8.2.6 Actual Treatment

The subjects' actual treatment will be derived from exposure data. If a subject receives a study treatment that is different from the planned treatment for the entire time of treatment, then actual treatment is the treatment actually received. In the event that a subject receives both CSL312 and placebo, the subject will be included in the CSL312 group for this analysis set. Subjects receiving only placebo will be included in the placebo group.

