12.2 Deriving and Summarizing Pharmacokinetic Parameters

For subjects belonging to the PK Analysis Set, the PK parameters provided in [Appendix 15.1](#) will be determined, if applicable, from plasma concentration-time data for CSL312.

The PK parameter derivation including imputation of the values BLQ and missing data will be conducted in accordance to [PK-GDL-01](#) which gives guidance on how to derive PK parameters in the presence of missing data. The PK parameters will be calculated by standard non-compartmental analysis using actual sampling times and actual doses.

The following PK parameters will be summarized after SC administration of CSL312 at each SC dosing interval:

Variable	Statistical Parameters:
C _{trough} after first, second and third SC dose; C _{max} after last SC dose; AUC _{0-tau} after last SC dosing interval	n, arithmetic mean, SD, CV%, minimum, median, maximum, geometric mean and geometric CV%
T _{max} after last SC dose	n, minimum, median, and maximum

The following PK parameters will be derived and summarized after the IV administration of CSL312:

Variable	Statistical Parameters:
C _{max} C _{trough}	n, arithmetic mean, SD, CV%, minimum, median, maximum, geometric mean and geometric CV%
T _{max}	n, minimum, median, and maximum

All PK parameters will be reported to at least 3 significant digits, but to no more significant digits than the precision of the original data.

A by-subject listing of CSL312 PK parameters based on the PK Analysis Set will be provided.

13 Pharmacodynamic and Biomarkers Analyses

Unless otherwise specified, analyses in this section will be based on the PD Analysis Set.

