13.1 Pharmacodynamic Analyses

The absolute change from baseline in FXIIa-mediated kallikrein activity over time will be calculated for each subject. The comparison of primary interest is the change from baseline at Day 92 (Week 14). The change from baseline will be compared between CSL312 and placebo using a mixed-model repeated measure (MMRM) analysis, with treatment group and visit as fixed effects, and baseline as a covariate. Interactions with visit will be included for treatment group and baseline. The analysis will be implemented by using SAS PROC MIXED. A restricted maximum likelihood (REML) approach will be used. An unstructured variance-covariance structure will be used to model the within-subject errors. This variance-covariance matrix will be estimated across treatment groups. If the model fails to converge, a heterogeneous Toeplitz structure (the TOEPH option in SAS PROC MIXED) will be used. The Kenward-Roger approximation will be used to estimate denominator degrees of freedom and adjust standard errors. Mean difference in least square means (LSMeans) between treatment groups and its 95% confidence interval will be provided at each time point, assuming that the data is normally distributed. If the data are not normally distributed by visual inspection of residual plots (QQ plots), an appropriate data transformation, log transformation, may be done.

FXIIa-mediated kallikrein activity will be summarized by nominal time point with the following descriptive statistics: n, mean, SD, %CV, minimum, Q1, median, Q3, maximum, geometric mean, geometric %CV, and percent below the limit of quantification (% BLQ).

Individual observed FXIIa-mediated kallikrein activity-time profiles will be plotted using actual sampling times. Mean (\pm SD) observed FXIIa-mediated kallikrein activity-time profiles will be plotted by using nominal (planned) time points.

The absolute change from baseline, percent change from baseline, and percent of baseline of FXIIa-mediated kallikrein activity over time will be summarized using descriptive statistics as done for the observed values of FXIIa-mediated kallikrein activity. The absolute change from baseline and percent of baseline of FXIIa-mediated kallikrein activity will also be presented graphically by treatment group as done for the observed FXIIa-mediated kallikrein activity.

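### The between-arm FVC comparison is grouped by treatment received, with no as-randomised analysis, and the grouping for kallikrein, PD and biomarkers is not stated

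*SAP*

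**What the plan says.** **FVC.** SAP 13.2.1 compares change from baseline in FVC and percent predicted FVC between groups by MMRM, with LSMean differences and 95% confidence intervals, and counts subjects with declines of at least 5% or 10%. Its population statement is "The Safety Analysis Set will be used for this analysis". Protocol 10.3.7.2 names the same set.

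**Grouping in that set.** SAP 6.2 states that "analyses will be based on the actual treatment received", and Protocol 10.2.2 says the same. SAP 8.2.6 adds the rule for mixed exposure: "In the event that a subject receives both CSL312 and placebo, the subject will be included in the CSL312 group for this analysis set". It then limits the other arm: "Subjects receiving only placebo will be included in the placebo group".

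**Kallikrein, PD and biomarkers.** SAP 13 opens with: "Unless otherwise specified, analyses in this section will be based on the PD Analysis Set". For kallikrein activity, SAP 13.1 says: "The change from baseline will be compared between CSL312 and placebo using a mixed-model repeated measure (MMRM) analysis". SAP 6.4 defines the population by membership only: "The PD Analysis Set is defined as subjects in the Safety Analysis Set for whom analysis results are obtained for" at least one exploratory biomarker. It does not say whether subjects are grouped by randomised or by actual treatment.

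**What is absent.** The only sets are Screened, Safety, PK and PD. Randomised treatment appears in the disposition summaries (SAP 9.1) and in by-subject listings (SAP 9.1 and 10.1). No as-randomised analysis of FVC or kallikrein is planned, not even as a sensitivity analysis.

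**The concern.** Grouping by treatment received is the usual choice for safety tables. For a between-arm comparison of outcome it gives up what randomisation provides, because arm membership then depends on something that happened after allocation. Under mixed dosing the rule also works in one direction only. A placebo-randomised subject with one CSL312 dose moves, while a CSL312-randomised subject with one placebo dose stays. (A subject given the wrong product throughout would move either way.)

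The FVC comparison carries some weight even though it is exploratory. Protocol 8.1.5 says: "This study will determine if the FVC is altered by treatment with CSL312 over a 14-week period in patients with IPF". Protocol 1.3 says the study is meant to support decisions on further development. SAP 10 describes FVC as an exploratory efficacy endpoint. If dosing errors cluster by site, or relate in any way to prognosis, the as-treated contrast absorbs that.

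**Working it through.** **1. Trace the rule for FVC.** SAP 13.2.1 and Protocol 10.3.7.2 point to the Safety Analysis Set. SAP 6.2 and Protocol 10.2.2 group it by actual treatment, and SAP 8.2.6 sends mixed exposure to CSL312. Each step is explicit.

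**2. Trace the rule for kallikrein.** SAP 13 points to the PD Analysis Set, which SAP 6.4 makes a subset of the Safety set. The chain stops there. SAP 8.2.6 refers to an analysis set without naming it, and SAP 11 states treatment received only for the safety analyses. As-treated grouping is the likely reading, but it is not written down.

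**3. Arm sizes.** The plan's own figure reproduces: 70 / (1 - 0.12) = 79.5, rounded up to 80, or 40 per arm. In reverse, 80 x 0.88 = 70.4, about 35 evaluable per arm. Regrouping by randomised arm leaves these unchanged.

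**4. Effect of moving one placebo subject.** The documents give no misdosing rate, expected FVC change or SD, so every mL value here is an assumption. Take n = 40 per arm, mean change -60 mL on placebo and -30 mL on CSL312 (difference 30 mL as randomised), and let the moved subject's change be x:

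- placebo mean = (40 x (-60) - x) / 39
- CSL312 mean = (40 x (-30) + x) / 41

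| x (mL) | Placebo mean | CSL312 mean | As-treated difference |
|---|---|---|---|
| -60 (placebo mean) | -60.0 | -30.7 | 29.3 |
| -300 | -53.8 | -36.6 | 17.3 |
| +180 | -66.2 | -24.9 | 41.3 |

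The difference is unchanged where (x + 30)/41 + (x + 60)/39 = 0, so x = -3630/80 = -45.4 mL. A moved subject who declines more than that narrows the gap; one who declines less, or improves, widens it. At 35 per arm the -300 mL case gives (-1050 - 300)/36 - (-2100 + 300)/34 = -37.5 + 52.9 = 15.4 mL. The choice of subject drives the result far more than n does. These are raw means; the MMRM also adjusts for baseline.

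**5. The same in relative terms, at 35 per arm.**

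- If k moved subjects respond like placebo, the contrast shrinks by 1 - 35/(35 + k): 2.8% for k = 1 and 10.3% for k = 4.
- With no drug effect, one moved subject lying 1 SD from the placebo mean shifts the contrast by 1/36 + 1/34 = 0.06 SD. Grouping as randomised gives no shift.

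**6. Would a moved subject resemble a treated one at Week 14?** Protocol 3.3.2 gives a half-life of about 18 days after SC injection. Under simple decay, ignoring absorption and using the same half-life for the IV dose, the fraction of one stray dose left at Day 92 is 2^(-days/18). That is about 3% for a Day 1 dose (91 days), 4% for Day 8 (84 days), 12% for Day 36 (56 days) and 34% for Day 64 (28 days). A placebo subject misdosed early would be counted as CSL312 at the Week 14 comparison with little drug remaining.

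**The case against.** **The risk is hypothetical and visible.** All doses are given at the site, treatment is assigned through the IRT at each dosing visit, and unblinded preparers are separate from the blinded staff who assess. No crossover is planned and no misdosing is reported. Randomised and actual treatment are listed dose by dose, so any case could be found. This stands, and it limits the priority. It does not remove the case for fixing the rule beforehand, since a re-analysis chosen after unblinding could look result-driven.

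**The stakes are low.** There is no primary hypothesis, FVC is exploratory, kallikrein is secondary, p-values are nominal and the sample size rests on feasibility. This also stands.

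**As-treated grouping has a rationale for PD.** The PD objective concerns CSL312 activity in a proof-of-mechanism study. Protocol 3.3.2 projects a median kallikrein inhibition of at least 90% at the nadir. Grouping by randomised arm leaves a misdosed subject in the placebo PD mean. The two groupings answer different questions, so a reader who inferred that the change has no downside would be going too far.

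**Kallikrein.** A reader might infer that the kallikrein comparison is stated to be as-treated. The documents do not say that. The FVC population sentence covers pulmonary function only, and the PD set has no grouping rule.

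**Conclusion.** For FVC the point holds on explicit text: the between-arm MMRM and the decline proportions are grouped by treatment received, mixed exposure goes to CSL312, and nothing as-randomised is planned. For kallikrein, PD and biomarkers the defect is an unstated grouping that probably follows the same rule.

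The size is nil if no subject is misdosed. Under the assumed means at 40 per arm, one moved subject yields 29.3 mL in the ordinary case and between 17.3 and 41.3 mL in deliberately influential ones, against 30 mL as randomised. A reader might take the fall to 17.3 mL as the expected effect, or conclude that the rule always works against the drug. Neither follows, because that subject is extreme and the direction depends on whether the change lies below or above about -45 mL.

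Protocol and SAP agree on the FVC set, so this is a design weakness and not a contradiction between them. The change is desirable but not essential.

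**What to change.** 1. In SAP 6 and 13.2.1, analyse the FVC MMRM and the FVC decline proportions by randomised arm in all randomised and dosed subjects.
2. In SAP 5, record this as a change from Protocol 10.3.7.2, which itself names the Safety Analysis Set. SAP 5 currently says there are no changes to the planned analyses.
3. In SAP 13, state that the kallikrein, PD and biomarker MMRMs are also grouped by randomised arm, with as-treated grouping as a sensitivity analysis.
4. In SAP 8.2.6, name the set to which the mixed-exposure rule applies, and keep as-treated grouping for safety, exposure and PK.

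The cost is a few sentences and one extra sensitivity analysis, with the drawback that a misdosed placebo subject stays in the placebo PD mean. Sample size is unchanged, and if dosing is clean the results are identical. The SAP is based on the protocol up to Amendment 2, and its Section 7.1 still treats COVID-19 vaccination as excluded although Amendment 3 removed that criterion. It needs an update in any case, and these edits can go in with it before database lock.

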15.1 Pharmacokinetic Parameters

Term	Definition [unit]	Calculation method
AUC _{0-tau}	AUC during a dosing interval (tau) [mass * time * volume ⁻¹]	Partial AUC from dosing time to dosing time plus Tau, using the linear up/log down rule
C _{max}	Maximum observed in plasma [mass * volume ⁻¹]	
C _{trough}	Observed concentration at the end of a dosing interval, immediately before the next dose administration [mass * volume ⁻¹]	
T _{max}	Time to reach maximum (peak) drug concentration in plasma [time]	

Signature Page

CSL312_2002 - Statistical Analysis Plan - v1 - 28Apr2022

Signed By	Date (GMT)
PPD [redacted]	03-May-2022 07:26:35
Approved-PPD [redacted] Approval	
PPD [redacted]	03-May-2022 10:24:05
Approved-PPD [redacted] Approval	
PPD [redacted]	29-Apr-2022 17:37:04
Approved-PPD [redacted] Approval	

--- Do Not Detach This Signature Page ---
